9.4. Safety Outcomes

The safety endpoints will be analyzed on an intention-to-treat basis. Safety outcomes will be reported as proportions and study groups compared using the Chi-square test or Fisher exact test, as appropriate.

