5.5. CD73 and Pro-inflammatory Cytokines

Multi-parametric flow cytometric analysis will be conducted on whole blood cells before study drug and on study-day 1 and study-day 3. Cells will be stained with CD4FITC-CD73PeCy7-CD8PerCP-CD3APC/Cy7 following fixation, permeabilized (BD Cytofix/CytopermTM) for intracellular staining with anti-IFN- γ (Clone 25723) or anti-TNF- α (Clone 6402) antibodies (R&D System/Bio-techne). The percentage of CD3+ T cells, CD4+ and CD8+ subpopulations, and CD73 expression on T lymphocytes will be determined within DAPI negative (viable) cell populations using MACSQuant. Myeloid cells will be analyzed to validate ceftriaxone's effect in lymphocytes. Neutrophils and monocytes will be gated and cell surface expression of CD73 and production of TNF- α assayed as described for lymphocytes.

6. Data Collection

Data will be collected to screen, recruit, and determine eligibility of prospective OHCA subjects. Prior to consent, certain information will be gathered for screening including name, date of birth, MRN, date/time of ICU admission, details surround the cardiac arrest, pre-existing terminal disease, medical

history, infection status, allergies, legal guardianship/prisoner, and medical status. Screening logs will be maintained and reasons for exclusion will be recorded. Data collection in REDCap will be completed for patients who are screened and/or enrolled in the PROTECT Study. REDCap is a secure, web-based application for data capture.⁶¹ Data collected may follow the International Liaison Committee on Resuscitation's Utstein criteria for OHCA.⁶² Data will be collected by research coordinators or study investigators from medical records, family members, ambulance run reports, or other sources. The REDCap data collection tool has been modified to ensure demographic data for EFIC patients is captured at XXXX. In addition to the data outline below, information on serious adverse events, study drug and trial completion will be collected.

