8.3. Study Drug Discontinuation

Study drug will be discontinued if:

- 1. Gallbladder toxicity occurs OR;
- 2. Withdrawal from the trial is in the patient's best interest OR;
- 3. Infection develops warranting a change in the antibiotic regimen OR;
- 4. Subject, POAHC, or LAR declines or revokes informed consent.

In the event of stopping the study drug, patients will continue to be followed for safety and efficacy outcomes, and will collect blood, sputum, and rectal samples for the inflammation and resistome assessments.

The independent DSMB will be empowered to stop the trial for under certain circumstances:

- 1. Efficacy
 - a. The trial will not be stopped for efficacy given the intermediate outcome of interest is pneumonia, rather than death or other concrete outcomes (e.g., stroke, myocardial infarction). Additionally, it will not allow for a complete assessment of the resistome or inflammation.
- 2. Harm
 - a. There is a statistically significant increased risk for serious adverse events, including *Clostridium difficile*-associated diarrhea, gallbladder toxicity, or type one hypersensitivity reactions, during the interim analysis of the first n=60 patients enrolled. The p-value threshold for harm will be set at 0.05.
- 3. Safety
 - a. Significant safety concerns emerge and the DSMB and IRB choose to pause or stop the trial.

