8.4. Study Specific Adverse Events

Adverse events are common in comatose OHCA patients occurring in >90%.⁶⁴ Adverse events may be the result of the clinical context or study drug. Adverse events that meet the "serious" definition in section 8.1 will be documented and assessed using the xxxx IRB reporting criteria.

Clinical events secondary to cardiac arrest will not be reported at any grade, since these are considered symptoms of the condition being studied. These may include:

- Septic shock
- Bleeding requiring transfusion
- Bradycardia requiring pacing
- Seizure confirmed on cEEG

Study specific adverse events that are expected secondary to ceftriaxone use will be reported as required per the definitions in section 8.1 and the table below. These include:

- Clostridium difficile-associated diarrhea
- Gallbladder toxicity

• Type one hypersensitivity reactions

Study Specific Serious Adverse Events	Definition
	Unexplained and new-onset ≥3 unformed stools
Clostridium difficile-associated diarrhea	in 24 hours with a positive Clostridioides difficile
	toxin gene polymerase chain reaction assay
	Diagnosed sonographically as an echo without
Gallbladder toxicity	acoustical shadowing suggesting sludge and the
	presence of ceftriaxone-calcium salt
	Acute symptom onset (minutes to hours)
	involving the skin, mucosal tissue, or both (e.g.,
	generalized hives, pruritus or flushing, swollen
Type and hypersensitivity reactions	lips-tongue-uvula) and at least one of the
Type one hypersensitivity reactions	following (a through c):
	a. Respiratory compromise
	b. Reduced blood pressure
	c. Signs of end-organ dysfunction

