9.1. Sample Size

Incidence of EOP without antibiotic prophylaxis is unclear due to low-quality studies, variable definitions for EOP, varying diagnostic criteria, and inconsistent reporting of antibiotic administration. Additionally, studies examine early antibiotics, which may be symptom-driven *or* prophylactic.

In the ANTHARTIC trial, the incidence of EOP at five days was 17% in the prophylaxis group and 31% in controls (absolute difference of 14%).³ When using their definition of EOP, the incidence at seven days was 19% in the prophylaxis group and 34% in controls (absolute difference of 15%).

In the TTM trial, pneumonia occurred in 52% of patients treated at 33°C and 46% in those treated at 36°C.⁶⁵ Pneumonia was not defined as early- or late-onset. In a post-hoc analysis, the incidence of pneumonia in patients admitted to centers administering antibiotic prophylaxis was 41% compared to 54% at centers that did not.⁶⁶ Clustering within centers was possible.

Using data from INTCAR, the incidence of pneumonia, which was not defined as early- or late-onset, was 33% with antibiotic prophylaxis. Accordingly, 60 patients will be randomized to each group (n=120 total). This provides 80% power at a two-tailed 5% level of significance to detect an absolute reduction in the incidence of EOP by 25%, from 55% to 30%.

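### No final between-arm comparison of serious adverse events is planned beyond three named events, and those three are tested without an effect estimate or confidence interval

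*Combined protocol and SAP*

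**What the plan says.** **Collection.** Section 6 (Data Collection) states that "information on serious adverse events, study drug and trial completion will be collected". Section 8.4 adds that adverse events meeting the serious definition "will be documented and assessed using the xxxx IRB reporting criteria", which is case-by-case handling and not a comparison of arms.

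**Interim.** Section 8.3 lets the DSMB stop the trial for harm under this condition: "There is a statistically significant increased risk for serious adverse events, including" *C. difficile* diarrhea, gallbladder toxicity or type one hypersensitivity, "during the interim analysis of the first n=60 patients enrolled. The p-value threshold for harm will be set at 0.05".

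**Final analysis.** Section 3.11.3 lists three safety outcomes: *C. difficile* diarrhea, type one hypersensitivity and gallbladder disease. Section 9.4 analyzes the safety endpoints by intention to treat and gives this method: "Safety outcomes will be reported as proportions and study groups compared using the Chi-square test or Fisher exact test, as appropriate". Section 11 (Publication) promises the safety outcomes in the main paper and does not mention SAEs.

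**Contrast.** Section 9.2 describes the effect on early-onset pneumonia by a risk ratio with 95% confidence interval, and 9.3 carries that approach over to the other infectious outcomes. Section 9.4 has no equivalent.

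**Filters on SAE reporting.** Section 8.1 keeps deaths out of SAE reporting unless the investigator judges them related to study drug or procedures. Section 8.4 leaves clinical events secondary to the arrest, such as septic shock or bleeding requiring transfusion, unreported at any grade.

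**The concern.** SAEs are part of the criterion on which the trial could be stopped at half enrollment, yet the plan has no analysis of them at completion beyond the three named events. An excess of some other serious event, or one that shows only when all 120 patients are in, has no prespecified place in the results. If such a comparison is made anyway, its form will be chosen after the data are seen.

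The second gap concerns the three events that are analyzed. With 60 patients per arm, a test on a small number of events will usually be non-significant whether or not the drug causes harm. Two proportions and a p-value invite the reader to take that as evidence of safety. The trial sets out to weigh risk against benefit (section 2.2) and describes ceftriaxone as a lower-risk antibiotic (section 2.4). An interval would show how far the data support that description.

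**Working it through.** **1. The plan's own figure.** Section 9.1 states: "Accordingly, 60 patients will be randomized to each group (n=120 total"). It adds: "This provides 80% power at a two-tailed 5% level of significance" for an absolute "reduction in the incidence of EOP by 25%, from 55% to 30"%. With pooled variance,

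n = [1.960·√(2·0.425·0.575) + 0.842·√(0.55·0.45 + 0.30·0.70)]² / 0.25² = (1.370 + 0.569)² / 0.0625 ≈ 60.2, or 61 per arm.

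Power at 60 per arm is 79.9%, so the figure reproduces. It concerns pneumonia only. The documents give no power for safety and no rate for SAEs or for the three named events, so every event rate below is an assumption.

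**2. Where SAEs appear.**

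| Step | SAEs in general | Three named events |
|---|---|---|
| Collected | Yes (section 6) | Yes |
| Interim harm rule, first 60 patients | Yes, on the ordinary reading of 8.3 | Yes |
| Final outcome list (3.11.3) | No | Yes |
| Final between-arm analysis (9.4) | No | Yes, all randomized patients |
| Effect estimate with interval | No | No |

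**3. What the planned test can show at 60 per arm.** When all events fall in one of two equal arms, the two-sided Fisher p-value for x against 0 is 2·C(60,x)/C(120,x).

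- 5 v 0: 2 × 5,461,512 / 190,578,024 = 0.057
- 6 v 0: 2 × 50,063,860 / 3,652,745,460 = 0.027

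So 6 v 0 is the smallest significant split with an empty control arm. With one control event, 7 v 1 gives p=0.061 and 8 v 1 gives p=0.032.

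**4. Power for a single event.** If the control rate is zero, power is P(X ≥ 6) with X binomial (60, p):

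- 5% v 0%: 7.9%
- 10% v 0%: 56.3%

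With a 1% control rate, exact Fisher power in the harm direction is 0.5% for 3%, 5% for 5% and 40% for 10% in the ceftriaxone arm.

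**5. What an interval would add.**

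- Take 5/60 v 2/60. Fisher's p is 0.44. The Wilson limits are 3.6% to 18.1% and 0.9% to 11.4%. Newcombe's 95% interval for the difference of 5.0 points is:
  - lower: 5.0 − √[(8.3−3.6)² + (11.4−3.3)²] ≈ −4.3 points
  - upper: 5.0 + √[(18.1−8.3)² + (3.3−0.9)²] ≈ +15.0 points
- Take 0/60. The two-sided 95% upper limit for the true rate is 1 − 0.025^(1/60) = 6.0%.

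**6. What a full-trial SAE comparison would add.** Exact Fisher power (two-sided p<0.05, harm direction) for assumed SAE rates:

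| Assumed SAE rates | 30 per arm (interim) | 60 per arm (final) |
|---|---|---|
| 20% v 40% | 30% | 60% |
| 30% v 50% | 26% | 54% |
| 40% v 60% | 26% | 54% |

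In these scenarios the comparison that is not planned has about twice the power of the one that is.

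**The case against.** **The trial does compare harm in all 120 patients.** A reader might infer that harm across the full trial goes uncompared, or that half the patients enter no SAE comparison. The documents do not support either. Section 9.4 compares the three named events by intention to treat. Section 9.3 compares day-28 mortality and the infectious outcomes. ICU and hospital mortality, non-pulmonary infection and functional outcome are listed secondary outcomes in 3.11.2. The gap is confined to SAEs outside the three.

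**Nothing says that SAEs will be left out.** This is correct. The point rests on an omission, not on a statement that they are dropped. Section 8.4 also tables exactly the three events as study-specific serious adverse events, so the interim rule could be read as mainly about them. In that case interim and final analyses nearly match. But the list in 8.3 is worded as non-exhaustive and 8.1 defines SAEs broadly. On the narrow reading, other SAEs would be compared at neither stage.

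**Oversight continues after the interim.** Section 8.2 has no end date for SAE reporting, 8.3 lets the DSMB and IRB act on safety concerns at any time, and the DSMB charter is a separate document not available here. This stands, and it means no lapse in patient protection should be inferred. It does not supply a planned final comparison.

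**An SAE count could mislead.** This stands and shapes the fix. Under 8.1 and 8.4, deaths not judged related and arrest-related events never enter SAE reporting, so the count must be read beside mortality.

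**Readers can compute intervals from the proportions.** True, and 9.4 does not forbid them. The objection lowers the cost of the change more than the need for it. Nor does an interval raise power; it shows how little a non-significant test excludes. A reader might also take the three events to be rare, but no rate in the documents supports that.

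**Conclusion.** The point holds in limited form. SAEs are collected and included in the 60-patient harm rule, but no final between-arm comparison of SAEs beyond the three named events is specified. Those three are compared in all randomized patients by test only.

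The Fisher threshold (6 v 0) and the 6.0% upper limit for 0/60 depend only on 60 patients per arm. The power figures also depend on assumed event rates. The conclusion, that a non-significant safety test here would be nearly uninformative, holds across the rare-event rates tried (1% v 3% to 5%, and 5% v 0%). It weakens at 10% v 0%, where power reaches 56%. The primary efficacy conclusion is unaffected.

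**What to change.** In 3.11.3 and 9.4, for all randomized patients by arm:

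1. Add two outcomes: patients with at least one SAE, and patients with at least one SAE rated reasonably or definitely related under the section 8.1 scale. Show them beside mortality, with a note that 8.1 and 8.4 exclude deaths not judged related and arrest-related events from SAE reporting.
2. Report each of these, and each of the three named events, as a risk difference with 95% confidence interval as the main summary, with the p-value secondary. Name the interval method. A Newcombe interval and Fisher's test can disagree near the boundary: for 5 v 0, where p=0.057, the lower limit is 8.33 − √[(8.33−3.61)² + 6.02²] ≈ +0.7 points.

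This is a free improvement: the data are already collected, and no stopping or treatment rule changes. The only cost is one more table and wide intervals that make the safety conclusion less definite. A combined count of patients with any of the three named events is optional.

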9.5. Resistome Assessment

Abundance of antibiotic resistance-associated genotypes in resistomes will be compared within and between treatment groups. If ceftriaxone or placebo alters resistomes, ANOVA will be performed across genotypes. The abundance of each genotype will be compared between ceftriaxone- and placebo-treated patients post-intervention by both Student's T test and $\chi 2$ to establish direct changes associated with ceftriaxone and whether those deviate from potential changes in resistomes due to ICU admission. All statistical analyses will be performed using GraphPad Prism 8 (GraphPad Software Inc). A p value <0.05 will be considered significant. To measure the acquisition of ARGs, the increase in number of ARGs relative to baseline samples were compared within each treatment group using the Wilcoxon Signed-Ranks test. In addition, the baseline number and changes in the number of ARGs targeting a prioridefined frequently administered (macrolides, beta-lactams, fluoroquinolones, sulfamethoxazole-trimethoprim, and vancomycin) and infrequently administered (tetracyclines, erythromycin, aminoglycosides, chloramphenicol, clindamycin, fosfomycin, quinupristin) antibiotics according to clinical practice guidelines were compared between treatment groups.^{67,68}

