5.4. CD73/ Adenosine-mediated T Cell Activation

Analysis of genes involved in T cell response will be performed with total RNA isolated from CD3+ lymphocytes after their incubation in the presence of vehicle, ceftriaxone, or in combination with AMP. Total RNA will be isolated using RNeasy Mini Kit (Qiagen) and cDNA will be generated using RT² Nano PreAMP cDNA Synthesis Kit (SABiosciences). Gene expression will be analyzed using Oligo GEArray[®] Human T-cell and B-cell Activation Microarray (SABiosciences, OHS-053). This panel of 113 genes includes CD28, CD3E, IL10, IL12B, IL18, IL27, NCK1, and NCK2 genes involved in regulation of T cell proliferation and regulators of Th1 and Th2 development such as IFNG, IL10, IL12A, IL13, IL4, IL5, ITGAX, TLR2, TLR4, TLR7, and 11TLR9.

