9.6. Inflammation Assessment

We expect to obtain 56.3 \pm 4.5 x 10⁶ of total white blood cells, containing 14.7 \pm 1.7 x 10⁶ mononuclear cells and 6.3 \pm 1.1 x 10⁶ of CD3+ T cells from 10 mL of blood. We will use approximately 1 x 10⁶ CD3+ T cells to determine direct effects of ceftriaxone on CD73 expression and adenosine generation. We will use approximately 3 x 10⁶ of CD3+ T cells to isolate mRNA for gene expression analysis after treatment with ceftriaxone. Approximately 2-3 x 10⁶ whole blood cells will be used for flow cytometric analysis. Statistical analysis will be performed using the GraphPad Prism 7.0 software (GraphPad Software Inc). Comparisons between groups will be performed using two-tailed unpaired t tests. Comparisons between several groups will be performed using one-way ANOVA followed by appropriate post-hoc tests. A p value <0.05 will be considered significant.

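### Sections 9.5 and 9.6 set no error control across resistance genotypes or the 113-gene panel, and each genotype gets two tests with no rule on which decides

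*Combined protocol and SAP*

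**What the plan says.** **Resistome (Section 9.5).** The section opens: "Abundance of antibiotic resistance-associated genotypes in resistomes will be compared within and between treatment groups." It continues: "If ceftriaxone or placebo alters resistomes, ANOVA will be performed across genotypes." What counts as altering a resistome is not defined. It then states: "The abundance of each genotype will be compared between ceftriaxone- and placebo-treated patients post-intervention by both" a Student's t test and a chi-square test. The threshold is given once: "A p value <0.05 will be considered significant." The section also plans two count-based analyses:

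- the increase from baseline in the number of antibiotic resistance genes (ARGs), tested within each arm by the Wilcoxon signed-rank test;
- the baseline number and the change in number of ARGs against two pre-defined groups of antibiotics, compared between arms with no test named.

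**Inflammation (Sections 5.4 and 9.6).** Section 5.4 measures gene expression in CD3+ lymphocytes after incubation with vehicle, with ceftriaxone, or in combination with AMP: "This panel of 113 genes includes CD28, CD3E, IL10" and others. Section 9.6 gives the only test rule that covers these data: "Comparisons between groups will be performed using two-tailed unpaired t tests." For several groups it uses one-way ANOVA with unnamed post-hoc tests. The threshold is again 0.05.

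For these analyses the document names no family-wise or false-discovery method, no test hierarchy, no primary resistome or inflammation measure, and no exploratory label.

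**The concern.** A per-test threshold of 0.05 limits error for one test. It does not limit error for a list of genes read together, and a list of genes is what a metagenomic survey and an expression panel produce. The two procedures that might seem to help do not:

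- The ANOVA across genotypes has an undefined trigger and does not gate the per-genotype tests.
- The post-hoc tests in 9.6 act across groups within one outcome, not across the 113 genes.

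Two tests per genotype with no deciding rule is a separate gap. It exists whatever the number of genotypes. When the t test and the chi-square disagree, the plan does not say whether the genotype has changed.

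The results matter. The resistome is in the trial's title. Section 2.7 hypothesises less T cell-mediated inflammation and no adverse effect on resistomes as judged by resistance genotypes. Section 11 puts both data sets in the main publication. Under the written rule, chance alone can produce genes that suggest prophylaxis selects for resistance, or that it protects, and the plan gives no way to weigh such a list against the hypothesis.

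**Working it through.** **The plan's own figure.** The documents give no error rate for these families. Their only power statement is for early-onset pneumonia in Section 9.1: 60 per arm, 55% against 30%, 80% power, two-sided 5%.

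n = [1.960 x sqrt(2 x 0.425 x 0.575) + 0.842 x sqrt(0.55 x 0.45 + 0.30 x 0.70)]² / 0.25² = (1.370 + 0.569)² / 0.0625 ≈ 60.2, so 61 per arm. Power at 60 per arm is 79.9%. The figure reproduces, and nothing below affects it.

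**Inputs.** The threshold is 0.05 (9.5 and 9.6). There are 113 panel genes (5.4) and two tests per genotype (9.5). The number of genotypes m is not stated, so a range is shown as an assumption.

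**Gene panel, one test per gene, all nulls true, tests at their nominal level.**
- Expected false positives: 113 x 0.05 = 5.65.
- Chance of at least one, independent tests: 1 - 0.95^113 = 99.7%.
- Equally correlated test statistics (simulated):

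| Correlation | Chance of at least one | Expected number |
|---|---|---|
| 0.3 | 95.9% | about 5.6 |
| 0.5 | 80.1% | about 5.6 |
| 0.7 | 51.3% | about 5.6 |

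Correlation lowers the chance of any false positive but leaves the expected number unchanged.

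**Gene panel, if the same donor's cells go into every culture condition (assumption).** An unpaired t test on paired cultures falls below its nominal level. With within-donor correlation r, the per-gene error is 2 x [1 - Φ(1.96 / sqrt(1 - r))].
- r = 0.3: error 1.9%, 2.16 expected false positives, chance of at least one 89%.
- r = 0.5: error 0.56%, 0.63 expected, chance 47%.
- r = 0.7: error 0.03%, 0.04 expected, chance 4%.

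The last two columns of each line take genes as independent.

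**Resistome, one time point, independent genotypes.** One test each gives 1 - 0.95^m. For the two-test rule, abundance was simulated as zero-inflated lognormal, with prevalence 10% to 80% and 40 or 60 per arm. The t test was applied to abundance and the chi-square to presence; that reading of the chi-square is an assumption. A positive on either test occurred for 6.5% to 8.8% of null genotypes.

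| m | One test each | Either test positive |
|---|---|---|
| 10 | 40% | 49-60% |
| 20 | 64% | 74-84% |
| 50 | 92% | 97-99% |
| 100 | 99.4% | not tabulated |

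With one test each, it takes 59 independent genotypes to pass 95%.

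**Price of strict control, for scale.** The difference detectable at 60 per arm with 80% power is (z for alpha + 0.842) x sqrt(2/60). At 0.05 it is (1.960 + 0.842) x 0.1826 = 0.51 SD. At the Bonferroni level 0.05/113 = 0.00044 it is 0.80 SD. A false-discovery rule is less severe than this.

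**The case against.** A reader might infer that false resistome and inflammation findings are almost certain. Several arguments stand against that.

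- **The genotype count is unknown.** Near certainty in the resistome needs a number that the documents do not give. At 10 or 20 genotypes the risk is substantial but not near certain. This stands.
- **Multiplying up the tests overstates the problem.** One could take 200 genotypes, two tests and two post-dose rectal swabs, and get 800 x 0.05 = 40 false positives. Section 9.5 says only post-intervention; it does not say that the per-genotype tests are repeated at each swab. The two tests also overlap. At one time point, 200 genotypes would give 200 x 0.065 = 13 to 200 x 0.088 = 17.6 flagged genotypes. The 200 is itself hypothetical. This stands.
- **The panel is a laboratory contrast.** Section 5.4 compares culture conditions, not trial arms. The panel figures say nothing direct about the CD73, adenosine and cytokine measures that carry the inflammation aim. Section 9.6 also does not state that each panel gene is tested separately; that is the natural reading of its general rule. This stands, and limits what 5.65 and 99.7% show.
- **Both tests are planned, and they may answer different questions**, such as mean abundance and presence. This is fair: selective reporting cannot be inferred from the text. The lack of a deciding rule remains.
- **Summary measures already exist in 9.5.** They do. None is designated as the basis for the conclusion.
- **Correction can hide harm.** False positives in the harmful direction work against the trial's own hypothesis, and stricter thresholds make a real rise in resistance harder to see. This is the best argument against a purely adjusted analysis, and the fix should answer it.

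None of these points supplies a rule for reading the lists of genotypes and genes.

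**Conclusion.** The concern holds in limited form, as a should-fix. The per-genotype and per-gene families are judged at an unadjusted 0.05, and the genotype family has two tests without a deciding rule and no stated size.

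For the panel, about 5.65 false-positive genes are expected. This assumes one test per gene, tests at their nominal level and no true effects. The 99.7% additionally needs independence. Paired cultures analysed as unpaired would lower both figures. For the resistome, the defensible statement is a range that depends on m, from about 40% at 10 independent genotypes to 99% at 100 with one test each. The documents do not support a claim of near certainty there.

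The primary pneumonia test and sample size are untouched. So are the safety outcomes listed in Section 3.11.3, which do not include resistome measures.

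**What to change.** **Section 9.5**
- State how the set of genotypes to be tested is defined.
- Name one deciding test per genotype. If the other is kept, call it supportive.
- Declare genotypes by Benjamini-Hochberg at a 5% false discovery rate within each specimen type and time point, and say which time points are tested.
- Rest the resistome conclusion on one pre-named between-arm summary, such as the change from baseline in number of ARGs. Section 9.5 already plans this within arms, and between arms for the two antibiotic groups. Name its test, specimen and time point.

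**Section 9.6**
- Apply the same false-discovery rule across the 113 genes for each named culture contrast.

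**Both sections**
- Report effect sizes with confidence intervals, and unadjusted p-values beside q-values.
- Label both per-gene families exploratory.

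**Cost.** This takes a few sentences in the SAP and a line of code, and no new data. Parts of 9.5 are written in the past tense. If results exist, the rule can still be applied to the full set of p-values, with a note of when it was adopted.

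The real price is less power to flag any single genotype, including a harmful one. Showing the unadjusted p-values and relying on the single summary measure offset this.

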4.1. Specimen Handling and Transportation

Sputum sample and rectal swab will be collected prior to study drug initiation and 72-96 hours after administration of first dose of study drug (after study drug has been completed). A third rectal swab will be collected 144-168 hours after administering first dose of study drug or earlier in the case of death, comfort measures only or hospital discharge, after which no study procedures will be conducted. Missing time points do not disqualify patient for study participation and is not a protocol deviation. Total nucleic acids will be extracted and resistomes determined by shotgun metagenomic sequencing using super high-throughput methods. COVID-19 considerations are outlined in Appendix 16.7. Samples from non-XXXX hospitals may be stored and transported under various conditions not listed above but that are acceptable.

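### Section 9.5 tests each genotype's abundance by both Student's t and chi-square with no deciding rule, and plans a conditional ANOVA across genotypes with no patient term

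*Combined protocol and SAP*

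**What the plan says.** Section 9.5 of the combined protocol and SAP sets the target: "Abundance of antibiotic resistance-associated genotypes in resistomes will be compared within and between treatment groups". The between-arm test for each genotype follows: "The abundance of each genotype will be compared between ceftriaxone- and placebo-treated patients post-intervention by both" Student's t test and chi-square. A joint test is conditional: "If ceftriaxone or placebo alters resistomes, ANOVA will be performed across genotypes". The threshold is the same throughout: "A p value <0.05 will be considered significant".

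Two further analyses concern the number of resistance genes (ARGs), not their abundance. The increase from baseline is tested within arms: gains "were compared within each treatment group using the Wilcoxon Signed-Ranks test". Baseline numbers and changes for genes grouped by antibiotic, frequently or infrequently given "according to clinical practice guidelines were compared between treatment groups", have no named test.

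The section does not state:
- what the chi-square counts (patients, genes or reads);
- whether the ANOVA has a patient term;
- how an altered resistome is recognised before the ANOVA is run;
- which result governs when the t test and the chi-square disagree.

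Section 4.1 adds repeat samples per patient. Rectal swabs are taken before study drug and at 72-96 hours, and then: "A third rectal swab will be collected 144-168 hours after administering first dose of study drug". A patient can therefore supply two post-treatment swabs.

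**The concern.** Abundance is a measured quantity with one value per patient and sample. A chi-square test needs counts of independent units, so the sentence cannot be carried out until someone chooses what to count. Section 2.5 gives a sequencing depth of 20 million reads, so pooling reads by arm is one way to follow the sentence literally. Reads from one patient are not independent observations.

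The ANOVA raises the same issue. Genotypes measured in one patient share that patient's flora, illness and antibiotic exposure. Without a patient term, the rows are treated as if they came from different people. The test is also reached only through an undefined gate, so another analyst could not reproduce the decision to run it.

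The resistome is in the trial's title. Section 2.7 hypothesises that ceftriaxone will not negatively affect it, and section 8.3 gives its complete assessment as one reason not to stop for efficacy. A spurious positive would read as harm. With two tests and no deciding rule, the conclusion can depend on which is quoted.

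**Working it through.** **1. The plan's own figure.** The only power calculation (section 9.1) is for early-onset pneumonia, 55% v 30%, two-sided 5%, 80% power. With pooled variance, n = [1.96√(2 × 0.425 × 0.575) + 0.8416√(0.2475 + 0.2100)]² / 0.25² = (1.370 + 0.569)² / 0.0625 ≈ 60.2, so 61 per arm. Power at 60 is 79.9%. The stated 60 reproduces, but it does not concern the resistome, for which no power is given.

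**2. Inputs.** From the documents: 60 per arm, 1:1, p<0.05 per test. The documents give no mean abundance, spread, share of zeros, number of genotypes or within-patient correlation. Everything below rests on assumed ranges for these.

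**3. Chi-square.** On reads pooled by arm, with negative-binomial counts of mean m and size k per patient, the variance is D = 1 + m/k times what the test assumes. The false-positive rate is about 2[1 − Φ(1.96/√D)].
- m = 5, k = 2: D = 3.5, 1.96/1.871 = 1.048, rate 29.5% (simulated 29.2%).
- m = 1,000, k = 0.2: D = 5,001, 1.96/70.72 = 0.028, rate 97.8% (simulated 97.6%).

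A second model (log-normal Poisson counts, log-SD 1.0 to 2.0, 0%, 30% or 60% zeros, 60 per arm) gives 72% to 95%. Under that model, chi-square on patients with or without the genotype gives 4.3% to 5.6% when 30% or 60% of values are zero, which is correct.

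**4. ANOVA.** For the arm effect with G genotype rows per patient and within-patient correlation r, treated as independent, D = 1 + (G − 1)r and the same formula applies. Simulated at 60 per arm:

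| Genotypes | r | D | Formula | Simulated | t test on one mean per patient |
|---|---|---|---|---|---|
| 10 | 0.05 | 1.45 | 10.4% | 10.0% | 5.0% |
| 10 | 0.30 | 3.70 | 30.8% | 31.5% | 5.6% |
| 20 | 0.10 | 2.90 | 25.0% | 24.6% | 5.0% |
| 50 | 0.05 | 3.45 | 29.1% | 28.0% | 4.7% |
| 50 | 0.30 | 15.70 | 62.1% | 63.4% | 5.9% |

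**5. Two tests, no deciding rule.** Suppose both are done properly, on per-patient abundance and on carriage. Calling a genotype significant if either has p<0.05 gave 8.8% (30% zeros) and 7.7% (60% zeros). A repeat run gave about 6.5% to 8.5%. The range is therefore about 6.5% to 9%.

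**6. Student's t, one value per patient.** At 60 per arm its false-positive rate was 2.1% to 4.7%. Power for a 2.5-fold rise, with the same share of zeros in both arms:

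| Zeros | Log-SD | t, raw | Mann-Whitney | t, log scale |
|---|---|---|---|---|
| 0% | 1.0 | 96% | 99.8% | 99.7% |
| 0% | 1.5 | 56% | 88% | 89% |
| 0% | 2.0 | 23% | 67% | 68% |
| 30% | 1.0 | 84% | 61% | 55% |
| 60% | 1.0 | 51% | 14% | 22% |

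The ordering reverses with the share of zeros, so no test is best throughout.

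**The case against.** A reader might infer that all three tests ignore the patient, that the plan's error rates are therefore wrong, and that a rank test should replace Student's t. The documents do not support this.

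- The sentence compares treated patients, so one value per patient is the natural reading of the t test, and its error is then not inflated.
- Section 9.5 never names reads as the unit. Section 4.2 calls resistance genes from assemblies and annotated genes, which lends itself to presence or absence per sample, and chi-square on that is valid. The same section computes coverage, so abundance could also be derived. Neither reading is excluded.
- The ANOVA's rows and error term are not described, so independence of rows is a possible reading and not a stated one. The number of genotypes is assumed. The simulated rates leave out the gate, which can only reduce how often the ANOVA produces a false positive overall, although it does not make the p-value valid when the test is run.
- Loss of power with Student's t depends on a distribution the documents do not give. Choosing a rank test over t is a trade-off, not the correction of an error.

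All of this stands, and it makes the large percentages conditional. It does not remove the point. The text applies chi-square to abundance, leaves two tests without a deciding rule, and runs the joint test only after an undefined finding. The Wilcoxon test does not fill the gap, because it is within-arm and on the number of genes. The between-arm comparison of gene numbers names no test.

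**Conclusion.** The point holds as a fault in how the resistome tests are specified. Chi-square is assigned to a quantity it does not test, two tests compete without a rule, and the ANOVA lacks both a patient term and a defined trigger.

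Against a nominal 5%, the false-positive rate is:
- about 29% to 98% if chi-square is run on reads pooled by arm;
- about 10% to 63% if ANOVA rows are treated as independent;
- about 6.5% to 9% if either of two properly conducted tests counts and zeros are common.

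The first two apply only under those readings, and all three rest on assumed data. Carriage chi-square and Student's t on one value per patient keep their error rates. No general claim about lost power is supported. The pneumonia analysis is unaffected. The section should be corrected, because the stated methods can be replaced by clearly better-defined ones at little cost.

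**What to change.** In section 9.5:

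- State that the patient is the unit of analysis, and name the post-treatment sample that supplies each patient's value.
- Name one deciding between-arm test of per-patient abundance for each genotype. Student's t, a log-scale model or a rank test could each serve. The choice should be made in advance, with the expected zeros and skew in mind.
- Use chi-square or Fisher's exact test only for the number of patients carrying the genotype, and label it supportive.
- Delete the conditional ANOVA. For genotypes jointly, use a patient-level permutation test or a mixed model with a patient random effect, run whatever the other results show.

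Part of section 9.5 is written in the past tense. If these analyses have already been run, the report should state which unit and model were used.

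The cost is SAP wording and code, with no new data. The downside is slightly more analysis work, and possibly software other than the GraphPad Prism named in section 9.5. SAS and R are already listed in section 9.2.
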